7.2.1.2 Descriptive Statistics

The primary endpoint will also be summarized (descriptive statistics) and stratified by:

- Investigational Site
- Age
 - Adults age 22 and older
 - Adolescents age 16-21
- Ethnicity
 - Hispanic/Latino
 - Non-Hispanic/Non-Latino
 - Subject refused
- Race
 - American Indian/Alaska Native
 - Black/African-American
 - White - anticipated maximum less than 80%
 - Native Hawaiian/Other Pacific Islander
 - Asian
 - Other
 - Subject refused
- Baseline BMI according to WHO criteria [World Health Organization, 2011]
 - Underweight subjects (BMI less than 18.5 kg/m
 - Normal weight subjects (BMI 18.5 to 24.99 kg/m²):
 - Overweight subjects (BMI 25.00 to 29.99 kg/m
 - Obese subjects (BMI 30.00 to 39.99 kg/m
 - Morbidly obese subjects (BMI greater than or equal to 40 kg/m²)
- Gender
 - Male
 - Female
- Diabetes Classification
 - Diabetes type 1
 - Diabetes type 2
 - Other diagnosis of Diabetes
- Duration of Diabetes
 - Duration of diabetes less than 20 years
 - Duration of diabetes greater than or equal to 20 years
- Hypoglycemic Unawareness Questionnaire
 - Patients with intact hypoglycemic awareness (95% confidence interval will be provided)

- Patients who have impaired hypoglycemic awareness (95% confidence interval will be provided)
- Transition Groups
 - Subjects who have been exposed to the 530G pump therapy with the TS feature ON for 7 days or less prior to screening
 - Subjects who have been exposed to the 530G pump therapy with the TS feature ON for 8 to 365 days prior to screening

7.2.2 Safety Analysis for Multi-Center Trial

All adverse events reported by the site per protocol for enrolled subjects will be summarized. The summary will include all adverse events and adverse events by: Insulin Pump Infusion set; Insulin administration and pump use; Sensor Use; Severe Hypoglycemia; Severe Hyperglycemia; Diabetic Ketoacidosis; Adverse Device Event; Serious Adverse Event and Unanticipated Adverse Device Effect. Adverse Events by Investigator will also be provided. No formal statistical analysis will be carried out.

In addition, data will be collected for a descriptive summary of device disposition; adverse events; device performance and user acceptance. Safety analysis will include a summary of the following:

All Adverse events to be collected include the following:

- Adverse Events related to the study device
- Adverse Events related to study procedures
- Serious Adverse Events (SAE)
- Unanticipated Adverse Device Effects (UADE)
- Incidence of Severe Hypoglycemia
- Incidence of Severe Hyperglycemia
- Incidence of Diabetic Ketoacidosis (DKA)

Adverse Events will be stratified by

- Age
 - Adults age 22 and older
 - Adolescents age 16-21
- Ethnicity
 - Hispanic/Latino
 - Non-Hispanic/Non-Latino
 - Subject refused
- Race
 - American Indian/Alaska Native
 - Black/African-American
 - White - anticipated maximum less than 80%
 - Native Hawaiian/Other Pacific Islander)
 - Asian
 - Other
 - Subject Refused
- Baseline BMI according to WHO criteria [World Health Organization, 2011]
 - Underweight subjects (BMI less than 18.5 kg/m)

- Normal weight subjects (BMI 18.5 to 24.99 kg/m²)
- Overweight subjects (BMI 25.00 to 29.99 kg/m²)
- Obese subjects (BMI 30.00 to 39.99 kg/m²)
- Morbidly obese subjects (BMI greater than or equal to 40 kg/m²)
- Gender
 - Male
 - Female
- Diabetes Classification
 - Diabetes type 1
 - Diabetes type 2
 - Other diagnosis of Diabetes
- Duration of Diabetes
 - Duration of diabetes less than 20 years
 - Duration of diabetes greater than or equal to 20 years
- Hypoglycemic Unawareness Questionnaire
 - Patients with intact hypoglycemic awareness (95% confidence interval will be provided)
 - Patients who have impaired hypoglycemic awareness (95% confidence interval will be provided)
- Frequency and average duration of hypoglycemic event (based on two weeks prior to the adverse event)
- The actual one-sided 95% upper confidence limit of severe adverse event incidence rate (DKA and severe hypoglycemia) will be calculated. Individual one-sided 95% confidence limit for DKA only and severe hypoglycemia only will also be provided. Please note: the planned analysis may not be adequate since we did not meet the defined minimum sample size requirement.

7.2.3 Secondary Endpoint for Multi-Center Trial

The mean change in A1C from baseline to 3-month, 6-month, 9-month and 12-month will be summarized individually for each of the three baseline A1C cohorts:

- A1C less than 7.0%;
- A1C between 7.0% to 9.0%;
- A1C greater than 9.0%

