## 7. Statistical Methods and Data Analysis

### 7.1. Multi-Center Trial

#### 7.1.1. Sample Size Calculation

##### 7.1.1.1. Sample Size for Primary Endpoint

The overall mean change in A1C from baseline to the end of study will be estimated and compared by a non-inferiority test with an A1C margin of 0.4% and a significance level of 0.025 (one-sided) with the CEP 266 study population. The null hypothesis will be rejected if the one-sided 97.5% upper confidence limit of the mean change in A1C is less than 0.4%

The hypothesis is mathematically expressed as:

Ho:  $\mu \geq 0.4\%$

Ha:  $\mu < 0.4\%$

Where 0.4% is the pre-specified non-inferiority margin,  $\mu$  is the mean of change in A1C (%).

Assuming the mean of change in A1C from baseline to the 12-month follow-up visit is zero, the standard deviation of change in A1C is 1%, SAS power and sample size calculator shows that a total of 100 subjects will provide over 95% power to detect the non-inferiority with a margin of 0.4% and with one-sided type I error of 0.025.

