**A1C Change:**

- The percentages of subjects with increased A1C and decreased A1C from baseline will be presented for each baseline A1C subgroup (less than 7%, 7% – 9% and greater than 9%) and overall.
- The distribution of subjects' changes in A1C will also be summarized by histogram for each baseline A1C subgroup and overall.

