5.2 Study Population of Multi-Center Trial

A total of 426 subjects have been enrolled in the study.

40 Investigational centers were activated across the United States. Selection was based on Investigator's experience and qualifications, availability of sufficient resources to carry out the required study procedures and the investigator's ability to recruit subjects into the study.

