6.1 Sample Size for Primary Endpoint

The overall mean change in A1C from baseline to the end of study will be estimated and compared by a non-inferiority test with an A1C margin of 0.4% and a significance level of 0.025 (one-sided) with the CEP 266 study population. The null hypothesis will be rejected if the one-sided 97.5% upper confidence limit of the mean change in A1C is less than 0.4%

The hypothesis is mathematically expressed as:

Ho: $\mu \geq 0.4\%$

Ha: $\mu < 0.4\%$

Where 0.4% is the pre-specified non-inferiority margin, μ is the mean of change in A1C (%).

Assuming the mean of change in A1C from baseline to the 12-month follow-up visit is zero, the standard deviation of change in A1C is 1%, SAS power and sample size calculator shows that a total of 100 subjects will provide over 95% power to detect the non-inferiority with a margin of 0.4% and with one-sided type I error of 0.025.

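### A1C change is summarized within cohorts cut on the same single baseline A1C it is measured from, so regression to the mean moves the cohort means even if TS does nothing

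*SAP*

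**What the plan says.** SAP 7.2.3 and Protocol 7.1.5 define the secondary endpoint as mean A1C change from baseline to months 3, 6, 9 and 12, which "will be summarized individually for each of the three baseline A1C cohorts" (below 7.0%, 7.0 to 9.0%, above 9.0%). Protocol 7.1.6 and SAP 7.2.4.1 reuse the same grouping: "The percentages of subjects with increased A1C and decreased A1C from baseline will be presented for each baseline A1C subgroup", together with histograms of change. In the commercial data, Protocol 7.2.1 and SAP 7.8.1 repeat the pattern, with subgroups by first A1C and change measured from first to subsequent A1C.

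The visit schedule (Protocol Section 11, Table 1) places the first A1C at Baseline Visit 1. The Visit 0 laboratory tests do not include A1C, so there is no second pre-follow-up value. The trial has no control arm, and neither document mentions regression to the mean.

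The 0.4% margin is set for the overall mean change, at "a significance level of 0.025 (one-sided) with the CEP 266 study population". The planning values are given alongside it: "Assuming the mean of change in A1C from baseline to the 12-month follow-up visit is zero", and "the standard deviation of change in A1C is 1" (in percentage points of A1C).

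**The concern.** A single A1C is the subject's usual level plus that day's deviation. Selecting values below 7% picks up subjects who were temporarily low, and selecting values above 9% picks up subjects who were temporarily high. At follow-up the deviation is redrawn, so the first group rises on average and the second falls. Because the selecting value is also the starting point of the change, the whole movement enters the reported cohort means.

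The study objective is to show that home use of TS is not associated with glycemic deterioration. Read at face value, the cohort table would suggest deterioration in well-controlled subjects and benefit in poorly controlled ones, whatever the device does. It could also hide a real rise in the above-9% cohort. If visit-to-visit correlation is constant, the full shift appears by month 3 and stays through month 12, so it would look like a sustained effect. The cohort results are likely to be read as safety evidence: this is the only secondary endpoint, and SAP 7.8.1 says the commercial A1C analysis addresses the primary and secondary safety endpoint in the approval conditions.

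**Working it through.** **1. The plan's own figure.** The inputs, from SAP 6.1, are margin 0.4, SD of change 1, true change 0, one-sided alpha 0.025 and n = 100. Power = Φ(0.4 × √100 / 1 − 1.96) = Φ(2.04) = 97.9% (97.7% with the t distribution). This agrees with the statement that "a total of 100 subjects will provide over 95% power to detect the non-inferiority with a margin of 0.4". The overall calculation is sound.

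**2. Model for the cohorts.** Baseline and 12-month A1C are taken as bivariate normal with the same mean μ, the same SD σ and correlation ρ, and no true change in anyone. Then

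- SD of change² = 2σ²(1 − ρ), so 1 − ρ = SD of change² / (2σ²);
- expected change given baseline x = (1 − ρ)(μ − x);
- shift below 7% = (1 − ρ) σ φ(a)/Φ(a), with a = (7 − μ)/σ;
- shift above 9% = −(1 − ρ) σ φ(b)/(1 − Φ(b)), with b = (9 − μ)/σ.

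The SD of change (1%) and the zero mean change come from the plan. **μ and σ are assumptions**, because the documents give no baseline mean or SD.

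**3. One case in full (μ = 7.5, σ = 1.2).** 1 − ρ = 1/(2 × 1.44) = 0.347.

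- Below 7%: a = −0.417, φ = 0.366, Φ = 0.338. The cohort starts 1.2 × 0.366/0.338 = 1.30 below the mean and rises 0.347 × 1.30 = **+0.45**.
- Above 9%: b = 1.25, φ = 0.183, tail = 0.106. The cohort starts 1.2 × 0.183/0.106 = 2.07 above the mean and falls 0.347 × 2.07 = **−0.72**.

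**4. Range of assumptions, SD of change 1% (below 7% / above 9%).**

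| σ | μ = 7.2 | μ = 7.5 | μ = 7.8 | μ = 8.0 |
|---|---|---|---|---|
| 1.0 | +0.46 / −1.10 | +0.57 / −0.97 | +0.68 / −0.84 | +0.76 / −0.76 |
| 1.2 | +0.38 / −0.81 | +0.45 / −0.72 | +0.53 / −0.64 | +0.58 / −0.58 |
| 1.4 | +0.32 / −0.63 | +0.37 / −0.57 | +0.43 / −0.50 | +0.46 / −0.46 |
| 1.5 | +0.29 / −0.56 | +0.34 / −0.51 | +0.39 / −0.46 | +0.42 / −0.42 |

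Over the same grid, 62 to 80% of the below-7% cohort would show an increase, against 11 to 33% of the above-9% cohort.

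**5. Sensitivity to the SD of change.** The shift scales with its square. At 0.7% the grid is multiplied by 0.49, giving a below-7% rise of 0.14 to 0.37. At 0.5% it is multiplied by 0.25, giving 0.07 to 0.19. Right-skewed baselines (mean 7.5 to 7.8, SD 1.0 to 1.4) at SD of change 1% give a rise of 0.27 to 0.64 and a fall of 0.55 to 1.19.

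**6. Would noise hide it?** "A total of 426 subjects have been enrolled in the study". If all had data, the grid puts 16 to 45% of them below 7%, about 68 to 190 subjects. The standard error at SD 1% is then 1/√68 = 0.12 down to 1/√190 = 0.07. At the planning SD the shift is well outside noise.

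**The case against.** **Nothing is tested by cohort.** This is correct. The cohort changes are only summarized, with no hypothesis, margin or success rule. A reader might infer that the below-7% cohort would fail non-inferiority, or that the primary result is compromised. The documents support neither reading: the 0.4% margin applies to the overall mean change, and sorting into cohorts leaves that mean untouched. What remains is the risk that cohort means are interpreted as effects of TS.

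**The size is assumed.** This is also correct. A reader might take a rise of 0.4 or more below 7% as a fixed consequence of the plan. It is not: 6 of the 16 cells above are below 0.40, and at SD 0.7% or less all of them are. The 1% is a planning value, and equal variance at both visits does much of the work. In the extreme case where change is independent of baseline and follow-up variance grows, the shift is zero at the same SD of 1%. Against that, the model in Protocol 7.1.3.1 gives each subject a constant random effect plus error and no random slope. With independent errors, that is the structure used here.

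**Re-sorting does not cure it.** Two alternatives look free of the artefact, but neither can carry a conclusion. Both were checked at mean 7.6, SD 1.2, SD of change 1.

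- *Visit 2 to Visit 5 change by baseline cohort* is null only if correlation does not decay with time. Under first-order autoregressive correlation it still gives +0.34 and −0.49, about 70% of the artefact. It also misses months 0 to 3.
- *Cohorts of the mean of Visits 1 and 5* need equal variances. With no effect, a follow-up SD of 1.1 gives about +0.13 and −0.20, and 1.3 gives about −0.12 and +0.19. A true +0.5 in subjects with baseline below 7% shows as only +0.28.

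**Conclusion.** The concern holds in direction and is conditional in size. One value defines the cohort and starts the change, with no control arm or repeat baseline, so the below-7% cohort is pushed up and the above-9% cohort down without any TS effect. With an SD of change of 1%, zero mean change, equal variances, baseline mean 7.2 to 8.0% and SD 1.0 to 1.5%, the shift is about +0.3 to +0.8 and −0.4 to −1.1. With an SD of change of 0.5 to 0.7%, the below-7% rise is about 0.1 to 0.4. The increased/decreased percentages and the commercial first-A1C subgroups have the same weakness. It limits what the secondary endpoint can be used to conclude. It does not affect the primary test, and it does not show that any cohort would cross a criterion.

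**What to change.** In SAP 7.2.3, 7.2.4.1 and 7.8.1, and Protocol 7.1.5, 7.1.6 and 7.2.1:

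1. Keep the planned tables. Add a statement that changes in cohorts defined by baseline or first A1C include regression to the mean and will not be used as evidence of TS benefit or harm.
2. Beside each cohort mean change, print the shift expected from regression to the mean alone: (1 − ρ) × (overall baseline mean − cohort baseline mean). In the trial, estimate ρ from the repeated A1C values through the mixed model's subject and residual variance components. In the commercial data, estimate it from the paired first and subsequent values. State the equal-variance, constant-correlation assumption.
3. Optionally add, as sensitivity tables only, Visit 2 to Visit 5 change by baseline cohort, and change by cohorts of the mean of Visit 1 and Visit 5 A1C, each with the limits described above.

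The cost is a few sentences and a few extra tables from data already scheduled. The drawback is that the expected shifts depend on the model.

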7.2.4 Descriptive Endpoints for Multi-Center Trial

Descriptive Summary Statistics will be provided.

7.2.4.1 A1C Change:

- The percentages of subjects with increased A1C and decreased A1C from baseline will be presented for each baseline A1C subgroup (less than 7%, 7% – 9% and greater than 9%) and overall.
- The distribution of subjects' changes in A1C will also be summarized by histogram for each baseline A1C subgroup and overall.

7.2.4.2 TS Metrics – Hypoglycemia Endpoints:

Hypoglycemic Event Incidence, where an event is identified by the following criteria within 4 hours that TS is activated:

- CGM value less than or equal to 70 mg/dL continuously for greater than 20 minutes
- The rate of change (defined by the change between two consecutive sensor glucose measurements) will be examined during the 10-minute time interval before reaching a sensor glucose value of less than or equal to 70 mg/dL. If any rate of change in sensor glucose is >5 mg/dl/minute, the event will not be counted
- When the time between two successive events is less than 30 minutes, they will be combined as one event

The above information will be repeated for hypoglycemia threshold at 40, 50, 60, 65 and 70 mg/dL with and without TS activation and will be summarized by Day (8:00am – 10:00pm) /Night (10:00pm – 8:00am) and TS Threshold Settings.

The hypoglycemic event incidence, duration and the percentage of time spent (below TS threshold setting) within 4-6 hours of suspend will also be summarized. The hypoglycemic event is identified as:

- CGM value below the TS threshold continuously for at least 20 minutes
- No evidence of patient intervention which includes meter BG, meal marker and insulin delivery change during the first 20 minutes when CGM value is below the TS threshold.
- When the time between two successive events is less than 30 minutes, they will be combined as one event

Data will be summarized for each baseline A1C subgroup (less than 7%, 7%-9% and greater than 9%) and overall.

7.2.4.3 TS Metrics – Hyperglycemia Endpoints:

Hyperglycemic Event Incidence, where an event is identified by the following criteria within 4 hours that TS is activated:

- CGM value greater than or equal to 180 mg/dL continuously for greater than 20 minutes.
- The rate of change (defined by the change between two consecutive sensor glucose measurements) will be examined during the 10-minute time interval before reaching a sensor glucose value of greater than or equal to 180 mg/dL. If any rate of change in sensor glucose is >5 mg/dl/minute, the event will not be counted
- When the time between two successive events is less than 30 minutes, they will be combined as one event

The above information will be repeated for hyperglycemia threshold at 180, 250, 300, 350 and 400 mg/dL with and without TS activation and will be summarized by Day (8:00am – 10:00pm) /Night (10:00pm – 8:00am) and TS Threshold Settings. The hypoglycemic event incidence, duration and the percentage of time spent (below TS threshold setting) within 4-6 hours of suspend will also be summarized. The data will be summarized for each baseline A1C subgroup (less than 7%, 7%-9% and greater than 9%) and overall.

7.2.4.4 **Device Utilization:**

- We will provide descriptive summary statistics of suspend event including frequency, mean change of SG values before and after the suspense.
- TS Setting ON/OFF
- TS Threshold Setting
- Number of occurrences and time of Insulin Delivery Suspension by TS suspension/manual suspension (unrelated to the threshold suspend feature)
 - Manual suspension
 - Temporary basal set to zero
 - Threshold Suspend without user acknowledgement
 - Threshold Suspend acknowledged by user and cancelled
 - Threshold Suspend acknowledged by user and confirmed
 - Threshold Suspend first acknowledged by subject and confirmed, the followed by a second Threshold suspend not acknowledged by the subject after the hypoglycemia repeat time has elapsed.
- Subject response to insulin suspension
 - Confirmatory SMBG compliance during TS (within 2 hours of alarm) by length of time after the alarm (every 30 min up to 4 hours from TS activation)
 - Length of time to acknowledge TS alert by day and night
 - Comparison of time of alarm, time to SMBG and effects on glycemia
 - Therapeutic change in basal insulin (within 2 hours of alarm)
 - Frequency of basal increase/decrease/no change;
 - Summary statistics of amount of basal increase/decrease
- Frequency of Sensor Dislodgement / Suspected Occlusion
- Early infusion set change (before 3 days)
- Frequency of infusion set changes
- Frequency of Infusion Set occlusion alarms
- Total suspend time including manual suspends, times when the subject sets a temporary basal rate of zero, and threshold suspends separately and together during the nighttime, daytime, and 24 hour periods.
- Frequency of repeated threshold suspends with 1) ≤ 15 minutes and 2) ≤ 60 minutes of basal insulin delivery between suspends.
- Repeated threshold suspends with total suspend durations of ≤ 1 hour, 1- ≤ 2 hours, 2- ≤ 4 hours, 4- ≤ 6 hours, etc. Please calculate “total suspend durations” as the sum of the durations of repeated suspensions with 1) ≤ 15 and 2) ≤ 60 minutes between suspends (intervening basal delivery time should not be included).

7.2.4.5 **CGM Metric:**

- CGM Adherence – average sensor-wear per week
- Comparison between CGM data and Glucose Meter data

7.2.4.6 **Device Performance**

- All complaints that are reported via the 24-hour HelpLine will be summarized and reported.

7.2.4.7 Effectiveness of educational materials

- Subject Questionnaire at Screening
- Subject Questionnaire After Training Session and Device Placement

7.2.4.8 Human Factors:

- Frequency of subject acknowledging the alarm and continuing the suspend, when the suspend occurred automatically (without subject interaction)
- Frequency of subject not continuing the Threshold Suspend and instead manually suspending insulin delivery or setting a temporary basal rate of zero

7.2.4.9 Questionnaires:

The following will be performed on each questionnaire:

- EQ-5D and EQ-5D-Y
 - Summary of changes in score from baseline to end of study will be performed.
- Low Blood Sugar Survey (Adult, Parent and Child)
 - Summary of changes in score from baseline to end of study will be performed.
- Subject Questionnaire at Screening and Subject Questionnaire after Training Session and Device Placement (training evaluation questionnaire)
 - Summary of answers that will be provided no more than 2 hours before and 2 hours after placement of 530 G pump in order to assess effectiveness of training materials.
- Hypoglycemia Unawareness Questionnaire
 - Summary of changes in score from baseline to end of study will be performed.

7.3 Center Pooling

Data will be pooled for analysis.

7.4 Handling of Missing Data

For ITT population, the missing data in A1C measurements will be handled by the multiple imputation approach using imputation regression method, where the independent variables in the regression model are age, gender, baseline HbA1C and BMI. The imputation will be performed five times using the MI procedure and the analysis results will be combined to form one inference using the MIANALYZE procedure in SAS 9.4. The primary analysis population for the change in A1C endpoint will be the ITT population with multiple imputations.

All available device data will be used for the analysis. No imputation will be applied for the device data.

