### 7.1.3.2. Sensitivity Analysis

Sensitivity analysis will be performed on the ITT population with multiple imputations. The missing data in A1C measurements will be handled by the multiple imputation approach using imputation regression method, where the independent variables in the regression model are age, gender, baseline A1C and BMI. In each imputed dataset, the missing A1C data will be imputed by  $\hat{y} + z\hat{\sigma}$ , where  $\hat{y}$  is the predicted value from regression,  $Z$  is a standard normal random variable,  $\hat{\sigma}$  is the estimated standard deviation of the random residual from the regression model. The imputation

will be performed five times using the MI procedure and the analysis results will be combined to form one inference using the MIANALYZE procedure in SAS 9.3.

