7.1.3.2 Completed Case (CC) Population

The Completed Cases (CC) population is all subjects who complete the trial.

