7.1.3.3 Efficacy Population

The primary efficacy analysis will be performed on the CC population.

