7.2 General Methodology

7.2.1 Primary Efficacy Analysis

A mixed effects model will be used to produce the estimate and confidence interval of the overall mean change in A1C while accounting for inter-site variability: The 97.5% upper confidence interval of A1C will be calculated and compared to the 0.4% non-inferiority margin with the CEP 266 study population. As for endpoint analysis, the proposed mixed effects model using all A1C measurements has more power than the model only using Change in A1C from baseline to one-year visit.

$$Y_{ij} = X_{ij}\beta + B_i + B_{ij} + \varepsilon_{ij}$$

where

$Y_{ij} = (Y_{ij1}, \dots, Y_{ij5})'$ is the A1C measurement vector for the jth subject in the ith site;

$$X_{ij} = \begin{pmatrix} 1 & 0 & 0 & 0 & 0 \\ 1 & 1 & 0 & 0 & 0 \\ 1 & 0 & 1 & 0 & 0 \\ 1 & 0 & 0 & 1 & 0 \\ 1 & 0 & 0 & 0 & 1 \end{pmatrix}$$

is a the covariate vector for the jth subject in the ith site;

$$\beta = \begin{pmatrix} \beta_0 \\ \beta_1 \\ \beta_2 \\ \beta_3 \\ \beta_4 \end{pmatrix}$$

is the coefficient vector, β_0 estimate the mean A1C at baseline, β_4 estimate the mean change of A1C from baseline to one-year visit;

$B_i = (b_{i1}, \dots, b_{i5})'$ is the random effect vector for the ith site;

$B_{ij} = (b_{ij1}, \dots, b_{ij5})'$ is the random effect vector for the jth subject in the ith site;

$\varepsilon_{ij} = (\varepsilon_{ij1}, \dots, \varepsilon_{ij5})'$ is the random error term;

“The mean of baseline A1C measurement is estimated by β_0 , mean of 3-month A1C measurement estimated by $\beta_0 + \beta_1$, ..., mean of 12-month A1C measurement estimated by $\beta_0 + \beta_4$, i.e., β_4 estimate the mean change of A1C from baseline to one-year visit; the 97.5% upper confidence interval of β_4 will be calculated and compared the 0.4% non-inferiority margin.”

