7.2.1.1 Sensitivity Analysis

Sensitivity analysis will be performed on the ITT population with multiple imputations. The missing data in A1C measurements will be handled by the multiple imputation approach using imputation regression

method, where the independent variables in the regression model are age, gender, baseline A1C and BMI. In each imputed dataset, the missing A1C data will be imputed by $\hat{y} + z\hat{\sigma}$, where \hat{y} is the predicted value from regression, Z is a standard normal random variable, $\hat{\sigma}$ is the estimated standard deviation of the random residual from the regression model. The imputation will be performed five times using the MI procedure and the analysis results will be combined to form one inference using the MIANALYZE procedure in SAS 9.3.

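### The SAP names two different primary populations for the multi-center A1C test, and neither analysis uses the interim A1C of subjects who leave

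*SAP*

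**What the plan says.** **Completers are primary.** SAP 7.1.3.3: "The primary efficacy analysis will be performed on the CC population". Protocol 7.1.2.3 says the same. SAP 7.1.3.2 defines the set: "The Completed Cases (CC) population is all subjects who complete the trial". In line with that, SAP 7.2.1.1 (and Protocol 7.1.3.2) gives ITT a secondary role: "Sensitivity analysis will be performed on the ITT population with multiple imputations".

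**Imputed ITT is primary.** SAP 7.4, for the same endpoint: "The primary analysis population for the change in A1C endpoint will be the ITT population with multiple imputations".

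**Imputation model.** Protocol 7.1.3.2 has a regression imputation "where the independent variables in the regression model are age, gender, baseline A1C and BMI". SAP 7.2.1.1 and 7.4 give the same four predictors. A1C measured at 3, 6 and 9 months is not among them.

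**Software.** SAP 7.2.1.1 has results "combined to form one inference using the MIANALYZE procedure in SAS 9.3"; SAP 7.4 has them "combined to form one inference using the MIANALYZE procedure in SAS 9.4".

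**Analysis model.** SAP 7.2.1 supports its choice by saying "the proposed mixed effects model using all A1C measurements has more power".

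**Who is in ITT.** Everyone enrolled, and SAP 7.1.1 and Protocol 11.1 define enrollment by signed consent.

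**The concern.** There are three linked problems.

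1. SAP 3 could be read as ranking the SAP over the Protocol for the final report. That does not help, because SAP 7.1.3.3 and SAP 7.4 sit in the same document and neither yields to the other. Whichever result is more favourable could be reported as the planned primary.
2. Both candidates set aside A1C values that the trial has collected. If subjects whose A1C is rising leave more often, the values that show the rise are dropped (completers) or ignored (imputation), and both estimates lean toward non-inferiority.
3. ITT as defined includes laboratory screen failures. Protocol 11, Table 1 does not list A1C among the screening labs, and A1C is first drawn at Visit 1. Protocol 11.3 lets laboratory failures exit by phone before that visit. They have neither the outcome nor its main predictor, and the plan does not say how to impute them.

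This is the multi-center trial's single confirmatory test. The commercial sub-study has its own A1C test (SAP 7.8.1), which is not affected.

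**Working it through.** **1. Statements side by side**

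| Place | Completers | ITT with imputation |
|---|---|---|
| Protocol 7.1.2.3, 7.1.3.2 | primary | sensitivity |
| SAP 7.1.3.3, 7.2.1.1 | primary | sensitivity |
| SAP 7.4 | not named | primary |

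**2. The plan's power figure (SAP 6.1).** Margin 0.4, SD 1, true change 0, N = 100, one-sided 0.025: Φ(0.4/(1/√100) − 1.96) = Φ(2.04) = 97.9%; by noncentral t, 97.7%. This agrees with the stated figure of over 95%. At the 426 enrolled (SAP 5.2), power exceeds 99.99%. Power is not the issue.

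**3. Precision against bias.** With SD 1, the distance from estimate to upper limit, t/√N, is 0.095 for N = 426 and 0.107 for 340 completers (80%). Precision differs little. Bias can matter more: if 75% complete with mean +0.2 and the other 25% average +1.0, the cohort mean is 0.75 × 0.2 + 0.25 × 1.0 = 0.40, which is the margin.

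**4. Interim values under the planned model.** With all five visits present and the Protocol's random intercepts, β4 is the simple mean 12-month change. In a numerical check β4 was 0.2584. Altering only the interim values left it at 0.2584 and moved its standard error from 0.048 to 0.060.

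**5. Simulation.** From the documents: N = 426, SD of change 1, margin 0.4, five visits, five imputations. Assumed: A1C SD 1.2, linear mean change, monotone dropout after the 3-, 6- or 9-month visit, dropout rate and mechanism; age, sex and BMI uninformative. There were 2,000 runs per case.

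- Structure A: the Protocol's random-intercept model. From 2 × 1.44 × (1 − ρ) = 1, ρ = 0.653, so change correlates with baseline at 1.44 × (0.653 − 1)/(1.2 × 1) = −0.42.
- Structure B: change independent of baseline (successive correlation 0.9), paired t. The implied 12-month SD is √(1.44 + 1) = 1.56.

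False claims at true change 0.40 (nominal 2.5%), with dropout following the last observed A1C change at log-odds 0.5 / 1 / 2 per 1% A1C:

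| Case | Completers | Imputation as written |
|---|---|---|
| A, 30% dropout | 28 / 73 / 98% | 12 / 36 / 71% |
| A, 10% | 8 / 16 / 37% | 5 / 9 / 17% |
| B, 30% | 63 / 99 / 100% | 58 / 98 / 100% |
| B, 10% | 14 / 36 / 76% | 14 / 35 / 75% |

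- Mean estimates, A at 30%: completers 0.32 / 0.26 / 0.18, imputation as written 0.35 / 0.30 / 0.25. The two verdicts differ in 16 / 37 / 27% of runs. In B at 30% both estimate 0.27 / 0.17 / 0.07.
- Hand check, A at slope 1: 70% of 426 is 298 completers, distance to the limit 0.114, and 0.26 + 0.114 = 0.374 < 0.4. A typical completer analysis therefore passes wrongly.
- With interim A1C in the imputation: estimate 0.40 and 2.1 to 3.2% false claims in all twelve cases. Random-intercept likelihood on all visits (A only): 2.2 to 3.0%. Unstructured likelihood: 2.1 to 3.7%.
- Dropout unrelated to A1C, 10% or 30%: completers 2.4 to 2.7%, imputation 2.1 to 2.5%, either one passing 2.7 to 3.1%.
- Dropout driven by baseline A1C only (log-odds 0.5 per SD, 30%, A): if lower-baseline subjects leave, completers 18.9%, imputation as written 1.9%. If higher-baseline subjects leave, completers 0.1%, and at a true change of 0.25 they pass in 31% of runs against 69% for the imputation.
- True change 0.25 or 0.30, 30% dropout unrelated to A1C (A): verdicts differ in 12% of runs by chance.
- True change 0, 30% dropout, slope 1: every version passes in 100% of runs.

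A second simulation with a different correlation structure (A1C SD 1, correlation 0.5 between baseline and month 12, dropout about 29%, log-odds 1 to 1.5) gave completers 78 to 97%, imputation as written 51 to 80%, and imputation with interim A1C about 3%.

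**The case against.** The strongest reply separates the contradiction from the missing-data method. Free choice between the two analyses costs little by itself: 2.7 to 3.1% against 2.5% when dropout is unrelated to A1C. The large error rates come from the methods, and a consistent plan naming completers would show them too. That is correct, and it is why settling the label is not enough.

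The large figures also rest on inputs the documents do not give. Protocol 11.9 provides for withdrawal when the investigator judges health or safety compromised, but does not mention A1C. Protocol 11.8 anticipates poor compliance and lost insurance or finances instead. So the direction is established under A1C-linked dropout, but the size is not. The 426 includes any screen failures; with an assumed 350 subjects, structure A at slope 1 and 30% dropout gives 61 to 64% for completers and 31% for the imputation, which leaves the conclusion unchanged. The effect of the screen failures themselves was not quantified.

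SAP 7.2.1 claims power, not protection from bias, and interim values do affect the standard error, so that sentence is not false. The result in step 4 needs all five visits, whereas completing the trial does not guarantee five A1C draws; missed draws were not modelled.

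Finally, four of the five statements agree, so editing one sentence in SAP 7.4 would end the contradiction. It would do so by keeping the analysis that had the higher or equal error rate in every case with A1C-change-driven dropout.

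**Conclusion.** The concern holds. The SAP gives two primary populations for one test and no rule for choosing between them; this needs no assumption. Both specified analyses also leave out interim A1C that bears on who leaves.

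The consequence is conditional. It is nil at the planned change of 0, and small if dropout is unrelated to A1C. If dropout follows rising A1C and the true change is at the margin, false claims range from 8% to 100% for completers and from 5% to 100% for the imputation as written, over assumed dropout of 10 to 30% and log-odds 0.5 to 2. Adding the interim A1C brings this back to 2.1 to 3.2%. When dropout depends on baseline alone, the imputation in SAP 7.4 is already close to nominal and is the better of the two. This must be fixed before the final analysis, because the decision rule for the only confirmatory test is not unique. The SAS version mismatch is editorial, but shows the two paragraphs were not reconciled.

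**What to change.** - Name one primary analysis, worded identically in SAP 7.1.3.3, 7.2.1.1 and 7.4 and Protocol 7.1.2.3 and 7.1.3.2.
- Base it on participating subjects (SAP 7.1.1) with a baseline A1C, using every measured visit. The smaller change is to keep the imputation in SAP 7.4 and add the 3-, 6- and 9-month A1C as predictors. The alternative is to fit the mixed model by likelihood to all available visits with a stated within-subject covariance; unstructured is the more robust choice, though the simulations do not show it to be necessary.
- Keep completers as a sensitivity analysis.
- Leave screen failures without a baseline A1C out of the A1C analysis and in the safety population.
- Cite one SAS version.

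**Cost.** Wording, one analysis-set flag and extra imputation predictors; no new data. Protocol 8 requires IRB approval of the protocol amendment. The result may be less favourable: in structure A (30% dropout, slope 1) at a true change of 0.30, imputation with interim A1C passes in 40% of runs and all-visit likelihood in 45%, against 99% for completers and 90% for the imputation as written. Enrollment was complete when the SAP was written, and interim reports go to FDA, although without hypothesis tests (Protocol 7.3). The change should therefore be dated and documented as made before the final analysis.
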